	they complete it within 24 hours. They will also receive a £5 gift voucher
	upon completion of the 7-month follow-up. Participants who report
	abstinence at 7-month follow-up will be offered another £5 gift voucher
	along with a carbon monoxide (CO) monitor for biochemical verification of
	their abstinence.
Randomisation	Those who are eligible and consent to participate in the trial will be
Kanaomisation	randomised after completing the baseline questionnaire. Randomisation will
	be 1:1:1 at individual level with no restrictions (i.e., no blocking) and will be
	generated by an online automated algorithm, which counts to ensure each
	intervention will be displayed equally.
Blinding	Participants cannot be masked to treatment allocation. The investigators will
Dillialing	be blinded to participants' treatment allocation until all data have been
	collected. The trial statistician will have no contact with participants
	throughout the trial and will remain blinded for the analysis.
Intervention	Control
	No specific medication recommendation arm
	Participants in this group will be advised to access the Smoke Free app using
	a unique link provided to participants in the no specific recommendation
	medication arm, where they will receive routine smoking cessation
	behavioural support during their quit attempt. One day after randomisation,
	they will receive an email to remind them to use the Smoke Free app for
	smoking cessation behavioural support. The Smoke Free app is a theory-
	driven and evidence-based smoking cessation app (15). The app is designed
	to support users through the first three months of their quit attempt by
	reinforcing motivation, tracking progress, and highlighting the benefits of a
	smoke-free lifestyle. It incorporates a range of behaviour change techniques,
	including goal setting, reward systems, trigger identification, and coping
	strategies, to help users manage cravings and sustain abstinence (15).

Interventions

Varenicline arm

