Participants who report 6-month continuous abstinence at the 7-month follow-up will be asked to measure their CO levels to verify their abstinence. This will be conducted via a video call with a researcher, using a CO monitor provided by the study team.

Debriefing will involve an e-mail sent after immediate completion of the final follow-up. It will thank participants for their help with the study and provide them with a contact e-mail for further information.

Withdrawal of participants

Participants will be informed that they may withdraw from the study at any time without giving a reason. Unless they withdraw consent, they will be followed up irrespective of smoking outcome or protocol violation. On the basis of the intention-to-treat principle, those who do not respond to endpoint follow-up attempts will be retained in the analyses. Their outcomes will be imputed using multiple imputation (and classified as non-medication users and continuing smokers in a sensitivity analysis). Participants who indicate that they no longer wish to take part in the study will be excluded from the analyses.

Analyses

Primary analyses: Medication use

The primary two comparisons will be as follows:

- Any versus no specific medication recommendation: The first primary analysis will compare the combined medication recommendation arms (varenicline and cytisine) to the control arm (no specific medication recommendation). This analysis will assess whether recommending any medication (varenicline or cytisine) increases medication use.
- Cytisine versus Varenicline recommendation: The second primary analysis
 will compare the cytisine recommendation arm to the varenicline
 recommendation arm among participants randomised to receive a
 medication recommendation. This analysis will determine if there is a
 difference in medication use between the two recommended
 medications.

Logistic regression will be used to model the binary outcome of medication use (yes/no), adjusting for covariates (sociodemographic and smoking-related characteristics at baseline). P-values will be calculated using Wald's test.

The models will include the treatment arms as predictors. To obtain marginal risk ratios (RR) and risk differences (RD) alongside 95% confidence intervals, we will use the *marginaleffects* package in R.

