To account for missing outcome and covariate data, we will use multiple imputation with chained equations (in *mice* package). Imputation models will include experimental group, covariates, self-reported abstinence, and biochemically-validated abstinence. We will assume data are missing at random (MAR), meaning that having missing data on a variable does not depend on the true value of the variable, after accounting for predictor variables included in the imputation model. If less than 10% of data are missing, we will create 5 sets of imputations; otherwise, we will create 20 sets of imputations. Each set will be analysed separately and estimates combined using Rubin's rule.

Secondary analysis: Smoking abstinence outcomes

Above analyses will be repeated for smoking cessation outcomes, defined above in the measures section. As with the primary outcome, multiple imputation using chained equations (the *mice* package in R) will be used to account for missing outcome and covariate data.

Smoking cessation data are often missing not at random, as people who relapse to smoking are generally less likely to complete follow-up. However, the usual way to account for missing not at random, assuming "missing=smoking" (where all individuals with missing follow-up data are assumed to have relapsed to smoking), has been shown to be too extreme in internet-based smoking cessation trials (28). Instead, sensitivity analyses will examine the degree to which violations in the MAR assumption affect results. Multiple imputation with delta-adjustment will be used, with the degree of adjustment ranging from none (delta=0; MAR analysis) to very large (delta=100, approximating the missing=smoking assumption).

	Simple unadjusted complete case and "missing=smoking" analyses will be included in supplementary files as these are often used in meta-analysis.					
	Cost effectiveness					
	First, we will use the smoking cessation outcome directly observed in this trial—comparing the proportion of participants who report having quit smoking across trial arms at follow-up. This will provide a trial-based estimate of the intervention's impact on quitting, which can be used to estimate the potential health benefits (e.g., quality-adjusted life years [QALYs] gained) associated with the intervention.					

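### The delta-adjusted sensitivity analysis for abstinence follows a single delta, so when response is similar across arms the risk ratio and p-value stay almost fixed by construction; letting delta differ by arm would close the gap cheaply

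*Protocol*

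**What the plan says.** The Protocol, under Analyses (Secondary analysis: Smoking abstinence outcomes), accepts that abstinence data are often not missing at random, because "people who relapse to smoking are generally less likely to complete follow-up". It rejects missing=smoking as the main approach because it is too extreme for internet trials, and says that "sensitivity analyses will examine the degree to which violations in the MAR assumption affect results". The tool is multiple imputation with delta adjustment, "with the degree of adjustment ranging from none (delta=0; MAR analysis) to very large (delta=100, approximating the missing=smoking assumption".

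The upper end is defined in the same paragraph as the case "where all individuals with missing follow-up data are assumed to have relapsed to smoking". The lower end is the main imputation analysis, described under Primary analyses: "Imputation models will include experimental group, covariates, self-reported abstinence, and biochemically-validated abstinence". The supplementary complete-case and missing=smoking analyses also apply one rule to all arms. No delta specific to an arm is mentioned.

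The same section on primary analyses plans both effect measures: "To obtain marginal risk ratios (RR) and risk differences (RD) alongside 95% confidence intervals". Under Blinding: "Participants cannot be masked to treatment allocation".

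**The concern.** The analysis is meant to show how far departures from MAR could alter the abstinence comparison. A comparison of arms is biased mainly when the link between outcome and non-response differs between them. If one delta is applied everywhere, abstinence among non-responders falls in all arms together. With similar response, the arm rates then shrink by nearly the same factor and their ratio hardly changes. A stable RR and p-value would follow from the algebra, yet could be reported as robustness.

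A difference between arms is conceivable here. Participants know their allocation, and only the recommendation arms are advised, and emailed, to use a named drug. Abstainers who followed that advice might, for example, be readier to report success than abstainers in the control arm. Observed quitting in the trial also feeds the first cost-effectiveness approach.

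**Working it through.** **Inputs.** The protocol gives no figure for this analysis, and no abstinence rate, response rate or scale for delta.

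- From Sample size: 292 per arm, that is 584 versus 292 in the pooled contrast. These are completers of the medication-use outcome. The arcsine formula for 10% versus 16.8% at 2:1 with 80% power gives 291.007 controls, rounded up to 292, and 3 × 292 = 876, so the stated total is reproduced.
- Assumed: the same 584 and 292 provide abstinence data; response r = 60% in every arm (50% to 70% as a range); abstinence among responders p = 12% (recommendation) and 8% (control); delta is subtracted on the log-odds scale.

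**Formulae.** Non-responder rate q(p, δ) = expit(logit(p) − δ). Arm rate = r·p + (1 − r)·q(p, δ).

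**Why the RR is flat.** At δ = 0 the arm rates are p₁ and p₀. At the missing=smoking end they are r·p₁ and r·p₀, so r cancels and the RR is again p₁/p₀. In between, a common shift keeps the non-responder odds ratio at (0.12/0.88)/(0.08/0.92) = 1.57. The non-responder RR therefore stays between 1.50 and 1.57.

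**Results at 60% response.** For example, at δ = 1, q is 4.78% and 3.10%. The arm rates are 0.6 × 12 + 0.4 × 4.78 = 9.11% and 0.6 × 8 + 0.4 × 3.10 = 6.04%. The common RR is 1.508; with delta in the recommendation arms only it is 9.11/8 = 1.14.

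| δ | RR, common | RD, common (points) | RR, recommendation arms only | RR, control only |
|---|---|---|---|---|
| 0 | 1.500 | 4.0 | 1.50 | 1.50 |
| 0.5 | 1.507 | 3.5 | 1.28 | 1.76 |
| 1 | 1.508 | 3.1 | 1.14 | 1.99 |
| 2 | 1.505 | 2.7 | 0.99 | 2.28 |
| missing=smoking | 1.500 | 2.4 | 0.90 | 2.50 |

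Across 50% to 70% response the common-delta RR stays within 1.500 to 1.511. The recommendation-only extreme gives 0.75 at 50% and 1.05 at 70%.

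**P-values (unadjusted Wald test on the log odds ratio).** Under MAR with 584 and 292 responders, p = 0.072. Under missing=smoking with the same events among 584/0.6 ≈ 973 and 292/0.6 ≈ 487, p = 0.079. With 13% versus 8% the values are 0.029 and 0.033.

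**Check by multiple imputation with Rubin's rules.** Assumed data: 64/584 versus 19/292 abstinent, 70% response. A common delta leaves RR at 1.67 to 1.69 and p at 0.039 to 0.040 along the whole path. A delta of 0.5 in the recommendation arms alone gives RR 1.50 and p = 0.11.

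**Unequal response.** At 60% (recommendation) versus 65% (control), with 12% versus 8%, the common path runs from 1.50 to 1.385. In the imputation check at 60% versus 70%, RR falls from 1.69 (p = 0.044) to 1.45 (p = 0.15). The path reacts when response differs.

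**What the missing=smoking end recovers.** If abstainers respond at rates a₁ and a₀ and the true abstinence rates are P₁ and P₀, that end gives (a₁·P₁)/(a₀·P₀). It equals the true RR when a₁ = a₀, however differently smokers drop out. Otherwise it is off by the factor a₁/a₀. The recommendation-only value at δ = 0.5 corresponds to a true rate of 10.26%, with abstainers in those arms responding at 0.6 × 0.12/0.1026 = 70% against 60% in control, and recommendation-arm smokers responding at 58.8%. Overall response is still 60% in every arm, so the common path stays near 1.50 although the true RR is 1.28.

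**The case against.** **The planned path is not blind to drop-out that depends on arm.** A reader might infer that such drop-out goes wholly untested, especially the case of relapsed recommendation-arm participants staying silent. That goes too far. Silence of that kind lowers response in those arms, and the common path then moves. Suppose abstainers respond at 60% in all arms and recommendation-arm response falls to 40%, with responders still showing 12% versus 8%. The path then runs 1.50, 1.27 (δ = 1), 1.12 (δ = 2) and 1.00 at missing=smoking, and 1.00 is the true RR. This objection stands and narrows the point. The unexamined case is an outcome-response link that differs by arm with little or no response gap. In the figures above it works mostly through recommendation-arm abstainers answering more often, and the larger deltas need strong differences (79% against 60% at δ = 1).

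**An equal delta is not written down.** Correct: it is the natural reading of one scale whose two ends cover all participants. A statistical analysis plan, not shown here, could add values by arm. But the protocol does state a method, and a plan that followed it as naturally read would not reach the unexamined case.

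**Not everything is flat.** The RD falls by 40% in relative terms (4.0 to 2.4 points), and the protocol reports it. It cannot change sign along the path, however, when response is equal.

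**The delta range.** A reader might fault values up to 100, since on the log-odds scale the result has settled by about 5. The protocol offers 100 only as an approximation to a limit and states no grid, so nothing follows from this.

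**Consequence.** The outcomes are secondary, the protocol already expects lower power for them, and in the main example p exceeds 0.05 throughout. This stands and limits the importance.

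**Conclusion.** The point holds in a limited form. Read as one delta for all arms, the planned analysis responds to differences in response rate. It cannot show sensitivity of the RR or p-value to an arm difference in the outcome-response link that leaves response rates similar. In that setting a stable RR is not evidence of robustness: it moves by less than 0.01 along the common path in the 60% example, whereas a recommendation-only delta of 0.5 takes it from 1.50 to 1.28. In the imputation example the same modest delta takes p from 0.040 to 0.11.

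The flatness under equal response is algebraic. The sizes rest on assumed response, abstinence rates and log-odds scale, and nothing in the protocol shows that such an arm difference will occur. The point concerns the abstinence outcomes only and is of minor to moderate importance.

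**What to change.** State in the abstinence analysis section that delta may differ by arm: recommendation arms versus control in the first contrast, and cytisine versus varenicline in the second. Use a small log-odds grid, such as 0, 0.5, 1, 2 and 3 plus the missing=smoking end, in each arm. Report RR, RD and p over the grid, with the smallest between-arm gap in delta at which the conclusion changes (the tipping point). Show response by arm beside it, so that readers can judge which cells are plausible. The planned equal-delta runs remain as the diagonal.

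The cost is a sentence or two of text, extra runs of the same imputation code and one supplementary table. No further data or participants are needed. A positive abstinence result may look less robust than it would along the common path.

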Power calculations were conducted using the *pwr* package in R. Assuming that 10% of participants in the control arm will report using a prescription smoking cessation medication (based on Smoking Toolkit Study data)(19) at 2-month follow-up, and that a digital recommendation will increase this to 16.8% (relative risk = 1.68), we estimate that at least 876 participants providing data on the primary outcome (i.e., reporting medication use or non-use at 2-month follow-up) would be required to detect this difference with 80% power, using a two-sided alpha of 0.05. This corresponds to 292 participants per arm in the 1:1:1 randomised trial, which is equivalent to a 2:1 ratio of participants receiving any medication recommendation (cytisine or varenicline) versus no recommendation (control).

Using these same sample sizes of primary outcome completers, we also estimated the minimum detectable effect size for the secondary comparison of medication use between the cytisine and varenicline recommendation arms. Assuming a 16.8% average medication use rate across the two groups and setting alpha to 0.05, the smallest detectable relative risk with 80% power is approximately 1.69 with 292 participants per group. These correspond to medication use rates of approximately 21.1% in the cytisine

	arm and 12.5% in the varenicline arm, an absolute difference of 8.6 percentage points.
	Recruitment will continue until at least this number of participants have
	provided data on the primary outcome (medication use at 2-month follow-
	up), in order to ensure adequate power for the primary analysis.
	Power to detect analogous effects on secondary smoking cessation outcomes
	will be lower due to loss to follow-up and expected low rates of quitting.
Recruitment	Participants will be recruited through the Smoke Free app.
	Participants will self-enrol into the study using a link that they will receive
	when they sign up to Smoke Free app (both to the free and premium version
	of the app) and will complete a web-based screening questionnaire, which
	assesses the inclusion and exclusion criteria.
	Participants will be informed that the study involves completing an initial
	online questionnaire (baseline questionnaire) and further online
	questionnaires two and seven months later (follow-up questionnaires).
Compensation	Participants will be informed at baseline that they will receive a £10 gift
Compensation	voucher upon completion of the 2-month follow-up, with an additional £5 if

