	Second, we will adopt an indirect approach, which combines the observed effect of the intervention on smoking cessation medication use in this trial with existing evidence from prior systematic reviews on the effectiveness of cytisine and varenicline for supporting smoking cessation (8). This will allow us to estimate the potential impact of the intervention on smoking cessation outcomes under the assumption that its primary mechanism of action is through increased medication use.					
	In both approaches, we will estimate the potential QALYs gained per user of the intervention, using a look-up table for QALYs associated with smoking cessation (29). These will be compared to the estimated cost of delivering the intervention to assess its cost-effectiveness. The intervention will be considered cost-effective if the cost per user does not exceed the value of the QALYs gained, using accepted UK cost-effectiveness thresholds(30).					
Discussion	This is going to be the first RCT conducted in UK involving cytisine.					
Governance and ethics	Ethical approval for the trial was obtained from the UCL Research Ethics Committee (1248).					
Finance	The study is funded by Cancer Research UK (PRCRPG-Nov21\100002). VB and JB are members of the Behavioural Research UK Leadership Hub which is supported by the Economic and Social Research Council under grant (ES/Y001044/1).					
References	 Brown KF, Rumgay H, Dunlop C, Ryan M, Quartly F, Cox A, et al. The fraction of cancer attributable to modifiable risk factors in England, Wales, Scotland, Northern Ireland, and the United Kingdom in 2015. British Journal of Cancer. 2018;118(8):1130-41. Office for Health Improvements & Disparities. Smoking Profile - Smoking and inequalities. In: Disparities OfHI, editor. 2023. Cahill K, Stevens S, Perera R, Lancaster T. Pharmacological interventions for smoking cessation: an overview and network meta-analysis. Cochrane Database Syst Rev. 2013;2013(5):Cd009329. Hartmann-Boyce J, Chepkin SC, Ye W, Bullen C, Lancaster T. Nicotine replacement therapy versus control for smoking cessation. Cochrane Database Syst Rev. 2018;5(5):Cd000146. 					

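### The cost-effectiveness rule gives a yes/no verdict from estimated values with no uncertainty attached, and feeds it from two approaches without saying which governs

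*Protocol*

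**What the plan says.** All of this is in the Protocol, Analyses, under Cost effectiveness.

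- Direct approach: "First, we will use the smoking cessation outcome directly observed in this trial", by comparing the proportions who have quit across the arms.
- Indirect approach: "Second, we will adopt an indirect approach, which combines the observed effect of the intervention on smoking cessation medication use in this trial with existing" systematic-review evidence on the two drugs, "under the assumption that its primary mechanism of action is through increased medication use".
- Common step: "In both approaches, we will estimate the potential QALYs gained per user of the intervention", from a published look-up table. "These will be compared to the estimated cost of delivering the intervention to assess its cost-effectiveness".
- Decision: "The intervention will be considered cost-effective if the cost per user does not exceed the value of the QALYs gained", "using accepted UK cost-effectiveness thresholds".

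No cost, threshold value or QALY gain per quit is given. The section does not mention an interval, a probability of cost-effectiveness or a sensitivity analysis. It names no base case. The 95% confidence intervals described under Primary analyses, and carried over to abstinence under Secondary analysis, belong to risk ratios and risk differences and are not tied to this rule.

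The Sample size section adds: "Power to detect analogous effects on secondary smoking cessation outcomes" will be reduced by loss to follow-up and low expected quitting. It gives no quit rate.

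**The concern.** The rule takes the estimated gain as if it were known exactly. If delivery is cheap, as is plausible for a digital recommendation, in-app advice and one email, the break-even quit difference is far smaller than the standard error of the estimate. The verdict then depends on little more than the sign of a noisy difference.

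One verdict is also drawn from two inputs that can point in different directions. The direct approach uses an outcome that the protocol itself says has reduced power. The indirect approach uses none of the trial's quit data. A flat or negative abstinence result could therefore stand beside a projection that passes the rule, and the protocol does not say which one is the conclusion. If that is settled after the results are seen, the choice is selective. This is the only rule in the document that turns the trial's results into a statement about value for money.

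**Working it through.** **The protocol's own figure.** The Sample size section has 10% against 16.8%, 2:1, two-sided 0.05 and 80% power. The arcsine effect size is h = 0.2011. Control n = (1.960 + 0.842)² × 1.5 / 0.2011² = 291.1, so 292 per arm and 876 in total. This reproduces. The protocol states no operating characteristic for the cost-effectiveness rule.

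**Inputs from the protocol.** 292 per arm; medication use 10% without and 16.8% with a recommendation.

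**Assumptions (not in the protocol).** Both recommendation arms pooled, 584 against 292; cost C of £1 to £5 per user, with £20 and £100 as checks; value V of £10,000 to £40,000 per quit; quit rate 5% or 10%; 6-point quit gain per extra medication user; quit and use differences independent. Fewer participants at 7 months would widen the standard errors below.

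**The rule as a formula.**
- Direct: met if quit difference × V ≥ C, so break-even is C/V.
- Indirect: met if use difference × 0.06 × V ≥ C, so break-even is C/(0.06 V).

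**Break-even against noise.**
- Direct: from £1/£40,000 = 0.0025 points to £5/£10,000 = 0.05 points. The standard error at 5% quitting is √[0.05 × 0.95 × (1/584 + 1/292)] = 1.56 points.
- Indirect: from £1/(0.06 × £40,000) = 0.042 points of use to £5/(0.06 × £10,000) = 0.83 points. The standard error at 10% use is √[0.10 × 0.90 × (1/584 + 1/292)] = 2.15 points.

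**Chance of meeting the rule with no effect on either outcome** (400,000 simulated trials per setting; ranges run over V and the quit rate):

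| Cost per user | Direct | Indirect | Both | At least one |
|---|---|---|---|---|
| £1 | 48–49% | 49% | 24% | 74% |
| £5 | 48–49% | 36–46% | 18–22% | 67–72% |
| £20 | 44–49% | 6–36% | 3–18% | 47–68% |
| £100 | 28–46% | 0–2% | 0–1% | 28–47% |

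The £1 row follows by hand, with each approach at about 0.49: both, 0.49 × 0.49 = 0.24; at least one, 1 − 0.51 × 0.51 = 0.74. If medication users quit more often, the two differences are positively correlated. Over a wider range of assumed quit rates (3% to 20%) and efficacy at near-zero cost, with ties counted either way, at least one is met 69–78% of the time and both 24–31%.

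**Use rises as planned, quitting does not.** The use difference is 6.8 points, with standard error √(0.168 × 0.832/584 + 0.10 × 0.90/292) = 2.34 points. At the least favourable £1-to-£5 setting, z = (6.8 − 0.83)/2.34 = 2.55, a 99% chance of passing. Simulation gives 99.4% to 99.8% over the range. The projected value at the lowest V is 0.068 × 0.06 × £10,000 = £41 per user.

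**Quitting truly falls from 5% to 4%.** At £1 and £10,000 per quit, the direct approach still passes 24% of the time.

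**The case against.** **Nothing says that either approach is enough.** A reader might infer that passing by one route suffices and quote 74% as the rate. The text says only that QALYs are estimated under both approaches. The 74% belongs to one of three readings. What stands is that the protocol does not choose among them.

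**Low cost is assumed.** The protocol gives no figure, and what will be costed (arm-specific app content, information on obtaining and using the drug, the email) is not itemised. The indirect rate drops fast as cost rises. This objection holds for the indirect approach. It has much less force for the direct one, which still passes 28% to 46% of the time at £100.

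**Deciding on expected net benefit is an accepted convention.** With zero effect and almost zero cost, true net benefit is close to zero, either sign is about equally likely, and a wrong call loses little. It would be wrong to read these rates as type I errors. But that convention needs one expectation, and here there are two with no order between them.

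**Handling of uncertainty may sit in an analysis plan that is not shown.** It may, and silence alone would not be a finding. However, the protocol does fix the decision rule, and adding intervals elsewhere would not change the verdict that the rule returns.

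**The indirect approach is openly a model.** The 99% scenario breaks its stated assumption about mechanism. A reader might go further and say that the indirect approach can never support a cost-effectiveness conclusion. The documents do not support that: it rests on a declared assumption and on review evidence. The point is only that it should be labelled as a projection and its rank fixed.

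**The analysis is ancillary.** Cost-effectiveness is not among the research questions or outcomes, and the trial's tests are unaffected. That limits the importance of the point.

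**Conclusion.** The point holds in this form: the protocol fixes a yes/no verdict on estimated values alone, and applies it to two approaches without naming the one that governs or saying what follows from disagreement.

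Its size depends on inputs that the protocol does not give. At £1 per user with no effect on either outcome, the chance of a favourable verdict is about 24%, 49% or 74%, according to whether both approaches are required, one is the base case, or either suffices. At £5 the direct approach alone still passes 48–49% of the time. With the planned rise in use and no change in quitting, the indirect approach passes at least 99% of the time at £1 to £5.

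These figures measure how little the bare verdict discriminates. They do not show that the protocol adopts an either-route rule or that delivery is nearly free. The change should be made, and before results are known, but it concerns a supporting analysis and not the trial's primary comparisons.

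**What to change.** Amend the Cost effectiveness section as follows.

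1. For each approach, report incremental net benefit per user with a 95% interval, and the probability of being cost-effective at a stated threshold. For the direct approach, carry the uncertainty of the multiply imputed quit difference. For the indirect approach, carry that of the medication-use difference and of the review effect.
2. Word the conclusion in terms of that probability and interval instead of a yes/no comparison of estimates.
3. Name the base-case approach before results are known. The trial-observed direct approach is the natural choice, with the indirect one labelled a model projection.
4. State that both are reported side by side if they disagree.

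This needs a wording change and a short computation from estimates already planned, plus the published interval of the review effect. No new trial data are needed. The price is a less decisive conclusion: with limited power for quitting, the direct approach will probably give a wide interval and a middling probability.
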